### ***3.2 Enrolment and Randomisation to Treatment***

Only eligible adults providing written informed consent, according to the protocol approved by the local ethics committee, will be enrolled into the trial.

Patients will be enrolled sequentially according to the randomisation list. After screening and baseline assessment, all participants will be randomised in a 1:1 ratio into either:

1. CPAP + VLED (Intervention) OR
2. VLED alone (Control)

This is an open label study; it is not possible to blind the study due to the nature of CPAP treatment.

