## ***1.5 Outline of the Proposed Research***

***Project Title:*** Cardio-metabolic health effects of CPAP treatment for sleep apnoea during weight loss: A Randomised Controlled Pilot Trial

***Objective:*** To determine in obese people with pre-diabetes, the efficacy of treating OSA with CPAP during weight loss, to achieve greater improvements in glucose tolerance (a measure of diabetes risk), abdominal fat loss and other cardio-metabolic measures at three months. All patients will be invited to attend a follow up visit at 12 months with reassessment of outcomes, after following a low glycaemic index (GI)/high protein diet and exercise program for nine months.

***Design:*** A three month Randomised Controlled Trial (RCT) in obese pre-diabetic patients with OSA randomised to a very low energy diet (VLED) (control) or CPAP plus VLED (intervention). Following the randomised controlled phase, patients will be re-assessed for OSA severity. Any patients with persistent OSA will commence or continue on CPAP treatment if recommended by their treating sleep physician. In addition, all patients will receive education about how to maintain a healthy weight using a low GI/high protein diet and exercise program. Optional support from a dietitian will be offered. All patients will be invited to attend a follow up visit at 12 months with reassessment of outcomes.

***Hypotheses:*** Treatment of OSA with CPAP during a VLED, compared with a VLED alone for three months, will better improve:

1. Glucose tolerance and HbA1c
2. Central Blood Pressure
3. Abdominal and total fat mass
4. Lipid profiles

***Patients:*** Female and male centrally or generally obese adults with pre-diabetes and moderate-severe OSA.

***Primary Outcome:*** Glucose tolerance, as measured by two hour blood glucose level following an oral glucose tolerance test, assessed at three months.

**Secondary Outcomes:** Abdominal and body fat, metabolic syndrome components (glucose, lipids, BP), insulin sensitivity, 24 hour blood glucose levels, 24 hour central blood pressure, health related quality of life and cost effectiveness measures.

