### **3. Study Design and Procedures**

#### ***3.1 Study Design***

Study Design and Duration:	A three month randomised controlled parallel group trial in obese pre-diabetic patients with OSA randomised to a VLED (control) or CPAP + VLED (intervention). The study incorporates a superiority framework. Following the randomised controlled phase, patients will commence usual clinical care of their weight maintenance and their OSA. At 12 months they will be invited to attend a follow up visit.
Outcome Measures:	Primary Outcome: Glucose tolerance as measured by an oral glucose tolerance test at three months. Secondary outcome measures of abdominal and body fat (determined from DXA scans), metabolic syndrome components (glucose, lipids, BP), health related quality of life and cost effectiveness measures will also be assessed.
Location:	Study procedures will be conducted at the Woolcock Institute of Medical Research, except the DXA scan which will be undertaken at the Charles Perkins Centre, University of Sydney.

- *The study timeline can be found in Appendix A.*

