#### ***Randomisation:***

Randomisation will take place at baseline. Secure randomisation will be achieved through Research Tools. Participants will be enrolled sequentially according to a computer generated randomisation list using a random block size (2, 4 or 6) that is not available to staff who enrol participants. A unique participant randomisation number will be assigned sequentially, in ascending order and will comprise a three digit number prefixed by “R” (e.g. R001, R002 etc.). This randomisation number will be used to internally identify the treatment group the participant is assigned to.

At randomisation, the randomisation module in Research Tools system requires that the trial coordinator enter a screening number and then confirm that the displayed participant name and DOB match the participant they intend to randomise. All previously entered eligibility data are then automatically assessed. If the participant meets all inclusion/exclusion criteria then the trial coordinator is able to commit online to automatically randomising the participant. Once this occurs, the participant is irrevocably allocated the next available randomisation number and previously concealed treatment assignment. Both the randomisation number and allocated treatment are then displayed and permanently recorded against that participant’s online record.

To ensure the participant’s anonymity, documents will use the participant’s unique participant screening and randomisation numbers.

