### ***Body composition (DXA scan)***

Dual Emission X-Ray Absorptiometry uses a very low dose of radiation. This scanning machine provides a measure of body composition that is practical within a clinical setting. (Protocol can be found in **Appendix G**). These scans will be performed at 0, 3 and 12 months time points at the Charles Perkins Centre by a trained technician.

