### ***Overnight Sleep Studies: Polysomnography (PSG)***

At three points during the study (screening, 3 and 12 months[if clinically indicated]) patients will undertake overnight polysomnography at the Woolcock Institute for the purpose of determining sleep apnoea severity measured primarily via the apnoea hypopnea index (AHI). This requires the attachment of leads to the patient in order to measure chest and abdominal movement, airflow at the mouth and lips, blood oxygen level, muscle tone, eye movements, heart rate and electrical activity in the brain. The study is scored using standard criteria.

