#### *b) To measure total body density:*

1. A correct total body image shows the patient's entire body. Ensure that the head, feet and arms are all shown in the image.
2. Make sure the patient's head is 3 cm below the horizontal line of the table pad. Use the velcro straps to secure the patient's knees and feet to prevent movement during the measurements.
3. When analysing the image make sure the cuts are correctly positioned:
  - Head. The head cut should be located immediately below the chin.
  - Left and right arm. Both arm cuts pass through the arm sockets and are as close to the body as possible. Ensure the cuts separate the hands and arms from the body.
  - Left and right spine. Both spine cuts are as close as possible to the spine without including the rib cage.
  - Left and right pelvis. Both pelvis cuts pass through the femoral necks and do not touch the pelvis.
  - Pelvis top. The pelvis top cut is immediately above the top of the pelvis.
  - Left and right leg. Both leg cuts separate the hands and forearms from the legs.
  - Centre leg. The centre leg cut separates the right and left leg

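### The open-label statement is wider than its reason: nothing masks the person who analyses the DXA regions, which leaves abdominal fat (part of hypothesis 3) open to avoidable reader bias

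*Protocol*

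**What the plan says.** Section 3.2 declares the trial open label without exception: "This is an open label study; it is not possible to blind the study due to the nature of CPAP treatment". The only general provision for staff who collect outcomes is training (section 3.8, Personnel training). No section says whether anyone who reads or scores an outcome is kept unaware of the arm.

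The parts of the protocol that bear on this are:

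- **Outcome.** Section 1.5 lists "Abdominal and total fat mass" as hypothesis 3 and names abdominal and body fat among the secondary outcomes. Section 3.1 says they come from DXA. The primary outcome is "Glucose tolerance, as measured by two hour blood glucose level following an oral glucose tolerance test, assessed at three months".
- **Who scans.** DXA is performed "at the Charles Perkins Centre by a trained technician", away from the institute where the other procedures take place (sections 3.1 and 3.8).
- **Reading step.** Appendix G instructs the analyst: "When analysing the image make sure the cuts are correctly positioned". It then lists cuts for the head, arms, spine, pelvis and legs.
- **Sleep study.** Section 3.8 says "The study is scored using standard criteria" and does not mention the scorer. Under Visit 7 in section 3.7, CPAP-arm participants stop CPAP for a week before the 3-month recording.
- **Identifiers.** Section 3.3 gives each person a screening number before allocation and a sequential randomisation number at allocation. Of the latter it says: "This randomisation number will be used to internally identify the treatment group the participant is assigned to". The allocated treatment is stored on the participant's online record.

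**The concern.** The sentence in section 3.2 moves from a treatment that cannot be disguised to a study that cannot be blinded. Those are different claims. A participant knows whether they use CPAP, and so do the staff who manage it. A person placing region boundaries on a stored image need not know.

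The distinction matters where a reading involves judgement. If the analyst knows the arm and expects CPAP to help, small choices about where the trunk and pelvic boundaries fall could lean the same way across participants. Such a lean does not average out, and with about 30 completers a modest systematic difference between arms could pass for a treatment effect on abdominal fat. Who is masked is a matter of design and conduct that has to be settled before scans are read, so a separate analysis plan would not normally supply it.

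**Working it through.** **1. Does the stated reason cover the readers?** The reason in section 3.2 is the nature of CPAP. Set beside each role:

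| Role | Would CPAP itself reveal the arm? | Basis |
|---|---|---|
| Participant | Yes | uses the device or does not |
| Staff managing CPAP and sleepiness | Yes | sections 3.8 and 4 |
| DXA analyst | Not from the image | separate site (3.1, 3.8); light gown (Appendix G) |
| Scorer of the 3-month sleep study | Not from the recording | week off CPAP beforehand (3.7, Visit 7) |

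The reason holds for the first two rows only. The protocol's own procedures make masked reading feasible for the other two.

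**2. Which outcomes can a reader move?**

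- *Two-hour glucose (primary):* a laboratory value with no reader step.
- *Total fat mass:* the Appendix G cuts divide one whole-body image. Moving a boundary takes tissue from one region and adds it to the neighbour, so the sum over regions stays essentially the same.
- *Abdominal fat:* a regional quantity. Appendix G names no separate abdominal region, but any value derived from trunk or pelvic regions depends on where those boundaries lie.
- *3-month sleep study:* not among the hypotheses, the primary outcome or the secondary outcomes in section 1.5. The exploratory models of OSA severity in section 4 use 12-month data.

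Only abdominal fat is both a listed outcome and open to this mechanism.

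**3. Illustration of size.** The protocol gives no reader-error figure, SD, effect size or alpha, so there is no stated figure on this point to reproduce. From the protocol I take 30 completers (section 4) and 1:1 allocation (sections 2.1 and 3.2), giving 30/2 = 15 per arm. My assumptions are a two-sided 5% test, a two-sample t-test in place of the planned mixed model, no true effect, and a systematic between-arm reader shift of *s* outcome SDs.

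- Degrees of freedom: 15 + 15 − 2 = 28; critical value 2.048.
- Noncentrality: *s* × √(15/2) = *s* × 2.739.
- False-positive rate: the probability that a noncentral t with 28 df exceeds 2.048 in absolute value.

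| Assumed shift (SD) | Noncentrality | False-positive rate (t) | Normal approximation |
|---|---|---|---|
| 0 | 0 | 5.0% | 5.0% |
| 0.1 | 0.274 | 5.8% | 5.9% |
| 0.2 | 0.548 | 8.3% | 8.5% |
| 0.3 | 0.822 | 12.5% | 13.0% |
| 0.5 | 1.369 | 26.2% | 27.8% |

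These rates show what a given shift would do. They are not evidence that any shift occurs.

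**The case against.** The best defence is that the protocol never says readers know the arm. The DXA technician works elsewhere and may in practice be unaware. DXA is largely instrument-derived; Appendix G fixes anatomical landmarks, and it asks for the same machine throughout and, where possible, the same measurer for each patient. The instruction on cuts could mean checking automatic placement rather than drawing by hand. Nothing in the protocol suggests that a boundary adjustment could move the outcome by as much as 0.5 SD.

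Most of this stands, and it limits the size of the concern. It does not supply a safeguard. Landmarks and a constant measurer reduce random variation between operators, but they do not prevent a lean by arm, and checking a cut is still a judgement.

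A reader might also infer four stronger things that the protocol does not support:

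- *That all of hypothesis 3 is exposed.* Total fat mass is not, because moving internal boundaries leaves the whole-body sum essentially unchanged.
- *That unmasked sleep scoring biases a trial outcome or settles who receives CPAP afterwards.* OSA severity is not a listed outcome, and section 1.5 makes CPAP after three months depend on the treating sleep physician's recommendation.
- *That the randomisation number discloses the arm.* It is a sequential number from a concealed list with random block sizes, and section 3.3 describes its link to the group as internal. The allocation sits on the participant's database record, to which the screening number also leads. Access to that record is what matters, not which number is on the scan.
- *That masking is free.* The protocol says nothing on cost and does not say who scores the sleep studies.

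**Conclusion.** The point holds in a narrow form. Section 3.2 applies to the whole study a reason that is valid only for participants and treating staff, and as a result nothing masks the analysis of DXA regions. The listed outcome at risk is abdominal fat, which is one part of hypothesis 3 and a secondary outcome. Total fat mass and the two-hour glucose primary outcome are essentially unaffected.

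The size of any bias is unknown. The false-positive rates of about 8%, 12% and 26% rest wholly on assumed shifts of 0.2, 0.3 and 0.5 SD, on an assumed two-sided 5% level and on a simple t-test. They should not be read as an estimate for this trial. The conclusion also assumes that the operator has some discretion over the cuts, which the Appendix G wording implies but does not quantify.

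This is a cheap improvement of low severity. It does not threaten the trial's main comparison.

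**What to change.** Reword section 3.2 so that the open-label statement is limited to participants and treating staff. Add text along these lines: *DXA scans will be analysed by existing staff who are not told the allocation. Where feasible, the 3-month sleep study will be scored in the same way. Scans and recordings will carry a code, and these staff will have no access to the allocation field in the trial database. Participants will be asked not to mention their arm, and any accidental unmasking will be recorded.* Cross-refer to this from the DXA and polysomnography entries in section 3.8 and from Appendix G.

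The sleep-study clause is supporting only, since that measure is not a listed outcome. It depends on a scorer being available who is not involved in the participant's CPAP care.

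The cost is a protocol wording change, a labelling code and a database access restriction, with no added visit or procedure. The downsides are a small administrative load and occasional unmasking when a participant talks about treatment.

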### ***3.3 Assignment to Treatment Groups***

#### ***Informed consent:***

Enrolment of participants into the trial will be performed by a combination of study doctors and coordinators as eligibility needs to be established. All participants will first be provided with a participant information sheet to read which includes details of all the study procedures, commitments and risks. The study staff member who enrolls the participant will also verbally explain the study to the participant in detail and provide opportunity to ask questions. All participants will then be asked to sign the informed consent form before proceeding to undergo formal screening.

#### ***Screening:***

All patients who undergo screening will be automatically allocated a screening number in ascending chronological order against which their personal details will be entered into the Research Tools™ database - including name, DOB, address and contact numbers. This number will be a three-digit number prefixed by "S" (e.g. S001, S002 etc.) and will be used to identify participants during the screening phase prior to randomisation. All data to allow assessment for trial eligibility will also be required to be entered into the Research Tools database.

#### ***Randomisation:***

Randomisation will take place at baseline. Secure randomisation will be achieved through Research Tools. Participants will be enrolled sequentially according to a computer generated randomisation list using a random block size (2, 4 or 6) that is not available to staff who enrol participants. A unique participant randomisation number will be assigned sequentially, in ascending order and will comprise a three digit number prefixed by “R” (e.g. R001, R002 etc.). This randomisation number will be used to internally identify the treatment group the participant is assigned to.

At randomisation, the randomisation module in Research Tools system requires that the trial coordinator enter a screening number and then confirm that the displayed participant name and DOB match the participant they intend to randomise. All previously entered eligibility data are then automatically assessed. If the participant meets all inclusion/exclusion criteria then the trial coordinator is able to commit online to automatically randomising the participant. Once this occurs, the participant is irrevocably allocated the next available randomisation number and previously concealed treatment assignment. Both the randomisation number and allocated treatment are then displayed and permanently recorded against that participant’s online record.

To ensure the participant’s anonymity, documents will use the participant’s unique participant screening and randomisation numbers.

### ***3.4 Concomitant medication, activities and procedures***

Any other medication considered necessary for the participant’s welfare and which does not interfere with the study objectives, assessment or treatment may be given at the discretion of the investigator. Allowed medications must be maintained at consistent dose as far as possible. Dose changes or the use of additional prescribed or non-prescribed medication should be recorded: noting drug, dosage, duration and reasons for use or dose change.

Any additional diagnostic, therapeutic or surgical procedures performed during the study period should also be recorded, including date, reason for and description of procedure and its outcome.

### ***3.5 Risks and Discomforts***

VLED: Minor side effects such as fatigue, constipation, diarrhoea, nausea, dizziness, headache, irritability and cold intolerance are usually transient and rarely prevent patients from completing the VLED program. Longer term side effects such as dry skin, hair loss and brittle nails usually subside with the re-introduction of a standard weight maintenance diet. In extreme cases vomiting, acute gout, acute gall bladder disease or cardiac disturbances (particularly if electrolyte disturbances) may preclude therapy.

[figure not shown]
Blood Test: There may be some discomfort from the venepuncture and cannular insertion at the site from which blood is taken. There is also a risk of some minor bruising at the site, which may last one to two days.

DXA Scans: This research study involves exposure to a very small amount of radiation. The dose from routine diagnostic X-ray and nuclear medicine procedures is 2 mSv to 20 mSv. The effective radiation dose from this study is about 0.54 mSv. At this dose level, no harmful effects of radiation have been demonstrated and the risk is very low.

In addition to the risks or discomforts listed here, there may be other known and unknown risks that are not disclosed here; patients should talk to the study doctor if they would like more information.

In addition, patients may have a right to take legal action to obtain compensation for any injuries or complications resulting from the study. Compensation may be available if their injury or complication is sufficiently serious and is caused by unsafe drugs or equipment, or by the negligence of one of the parties involved in the study (for example, the researcher, the hospital, or the treating doctor). Patients do not give up any legal rights to compensation by participating in this study.

### 3.6 Study Flow Chart

### 3.7 Schedule of study procedures

#### Visit 1: Screening (face-to-face)

Prior to conducting the screening visit, in order to determine eligibility, the investigator must:

- Provide the participant with written information on the study.
- Discuss study participation including answering questions about procedures, use of study devices and products, randomisation, potential risks and no guaranteed benefit from participation.

- Obtain signed consent.

If the investigator is satisfied that the person is potentially eligible, understands the nature and purpose of the study and is willing to participate fully in the study, he/she will be asked to sign the consent form. A signed informed consent must be obtained prior to the following procedures and tests being completed.

In order to determine eligibility, the following procedures need to be completed:

- Medical history and examination.
- Office blood pressure and heart rate.
- Venous blood sample, approximately 10mls of blood will be taken if a recent clinical blood test is not available.
- Current medication
- Resting ECG to rule out any potential contraindications to exercise
- Epworth Sleepiness Scale (ESS) and/or clinical report of debilitating daytime sleepiness.
- A previously recorded nocturnal polysomnogram (PSG) report is required to confirm patient eligibility. A PSG will be scheduled if it has not already been performed within the last 12 months or the patient has recently lost or gained >5% body mass.

Patients who satisfy eligibility criteria will proceed to visit 2 (week 0) baseline. **OPTIONAL:** Patients who pass this level may be enrolled directly into the study and have Visit 2 consecutively beginning the same day.

Patients demonstrating any absolute or relative contraindication to exercise through their resting ECG must be reviewed by the study doctor to determine if suitable for the study.

***Follow up with doctor:** For patients who do not pass the screening visit, a follow up visit should be organised with the clinic doctor.*

**Visit 2: Baseline assessment (0 weeks - face-to-face)**

Participants will need to attend this visit in the fasting state. The investigator will verify eligibility according to inclusion and exclusion criteria. If entry criteria are met, the volunteer can be enrolled in the study, and then commence the VLED. Each participant will be provided with written instructions on how to self-administer the VLED and with information on potential side effects to monitor.

The following examinations will be performed at this visit (not necessarily performed in this order):

1. Insulin sensitivity (MINMOD) which incorporates an oral glucose tolerance test
2. Total body fat & lean mass (DXA)
3. Anthropometry & Vitals
4. Bio-impedance spectroscopy
5. Blood markers
6. 4 Day food diary
7. Questionnaires
8. Lifestyle consultation
9. 24 hour continuous blood glucose monitoring
10. 24 hour central blood pressure monitoring

Participants will be provided with VLED packages and study staff will schedule a date for telephone support calls (Visit 3 and 4) after this face-to-face visit.

